6.2.3.1 Hemolytic Anemia

When there are clinical symptoms and/or laboratory signs of hemolytic anemia, dosing should be discontinued. Clinical symptoms are described in Section 7.1.3.1 and laboratory signs are described in Section 7.3.2. Follow-up laboratory monitoring is also

⁵ Administrative reasons (or other reasons not related to safety) are not to be considered safety reasons warranting treatment discontinuation.

described in Section 7.3.2. The medical monitor should be contacted to discuss whether or not resumption of dosing is indicated or for any other questions.

6.2.3.2 *Serotonin Syndrome*

Subjects are to be monitored at each visit by a medically qualified person for signs and symptoms indicative of potential serotonin toxicity, especially when initiating LMTM in this study or any medication with serotonergic potential. At each post-Baseline visit, subjects are to be evaluated by targeted physical and neurological examination and measurement of temperature, respiratory rate, blood pressure, and pulse (see Section 7.1.3.2 for guidance on assessment). Should serotonin syndrome (toxicity) be suspected clinically, treatment should be immediately discontinued. The event should be reported as an AESI and the medical monitor should be contacted for further guidance on subject management.

6.2.3.3 *Other Safety Reasons Requiring Dose Adjustment*

Treatment should be discontinued if the following treatment-emergent change occurs on ECG (based on the means of the three recordings) without other explanatory cause:

- QTcF interval > 500 msec: repeat ECGs should be obtained, in triplicate, within 2 weeks; if confirmed by the mean of the repeat ECGs, study drug should be discontinued pending further evaluation.

Other clinically significant changes in the ECG should be discussed with the medical monitor.

If renal concerns arise and the calculated creatinine clearance is < 30 mL/min, study drug should be discontinued.

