9.6.4 Electrocardiogram

ECG results will be provided by the central ECG reader. Tabular summaries and analyses are to be based on the central ECG data. Machine-read ECG results and interpretations are to be recorded in the eCRF and included in a separate listing; this also applies to any subsequent local interpretations if used to make dosing or patient management decisions.

ECG interval data will be summarized based on the average of the triplicate measures. All other study visit ECG data (interpretations or means of triplicate measurements if

performed for clinical reasons) will be summarized separately. ECG interval and ventricular rate data will be summarized using descriptive statistics for both the original values and the change from Baseline. Windows for each target visit will be used (additional details provided in the SAP). Parameters to be analyzed include heart rate (HR) and PR, QRS, QT, and corrected QT (using Fridericia's and Bazett's corrections), and RR intervals. Counts and percent of subjects in each result category will be tabulated. Overall interpretations of abnormality(ies) will also be tabulated, with subjects categorized by whether or not they have treatment-emergent abnormalities.

Subjects are also to be categorized and enumerated on the basis of QTc interval and change from Baseline as follows:

- QTcB/F outliers (in categories of > 450 to ≤ 480 , > 480 to ≤ 500 , > 500 msec)
- Change in QTcB/F outliers (in categories of > 30 to ≤ 60 , > 60 to < 90 , ≥ 90 msec)

All HR, interval data, and interpretations will be listed. Any new finding after Baseline will be categorized into diagnostic groups: rhythm, conduction, hypertrophy, arrhythmia, ischemia, infarction, other.

9.6.5 *Physical and Neurological Examinations and Serotonin Syndrome (Toxicity)*

Physical and neurological examination results obtained at Baseline (Visit 1) will be summarized by body system. Evaluation at subsequent visits will be summarized in a treatment-emergent fashion. Summaries will present the number and percentage of subjects with normal and abnormal observations by body system/parameter evaluated. By-subject listings will detail the abnormality(ies). Ratings for signs and symptoms of serotonin syndrome (toxicity) will also be summarized. For each target visit, the number of subjects for whom "yes" is answered for any of the signs and/or symptoms will be tabulated. A by-subject listing of results will also be prepared.

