## 4.2 Standard Calculations

Variables requiring calculation will be derived using the following formulas:

- **Baseline** - A baseline value, unless specified otherwise, is the last non-missing value recorded prior to the first dose of study drug in 020. If an assessment has the same date as the date of first dose of study drug in 020, the assessment will be counted as baseline (depending on the parameter, the data may have been acquired during the double-blind study of prior participation).
- **Study day** – For a given date (*date*), study day is calculated as days since the date of first dose of study drug in the open-label extension (*firstdose*):  
Study day =  $date - firstdose + 1$ , where  $date \geq firstdose$   
Study day =  $date - firstdose$ , where  $date < firstdose$
- **Days** – Durations, expressed in days, between one date (*date1*) and another later date (*date2*) are calculated using the following formula: duration in days =  $(date2 - date1 + 1)$ .
- **Weeks** – Durations, expressed in weeks, between one date (*date1*) and another later date (*date2*) are calculated using the following formula: duration in weeks =  $(date2 - date1 + 1) / 7$ .
- **Months** – Durations, expressed in months, between one date (*date1*) and another later date (*date2*) are calculated using the following formula: duration in months =  $(date2 - date1 + 1) / 30.4375$ .

- **Years** – Durations, expressed in years, between one date (*date1*) and another later date (*date2*) are calculated using the following formula: duration in years =  $(\text{date2} - \text{date1} + 1) / 365.25$ .
- **Body Mass Index (BMI)** -  $\text{BMI (kg/m}^2\text{)} = \text{weight (kg)} / [\text{height (cm)} / 100]^2$
- **Estimated Glomerular Filtration Rate (eGFR)** -  
 $\text{eGFR (mL/min/1.73 m}^2\text{)} = 175 \times (\text{serum creatinine in mg/dL})^{-1.154} \times (\text{Age in years})^{-0.203} \times (0.742 \text{ if female}) \times (1.212 \text{ if African American})$ .

Note that age on consent date is collected on the CRF and will not be calculated.

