#### **4.4 Visit Windows**

Since study visits do not always take place exactly as scheduled in the protocol, it is necessary to assign the actual observation times to “analysis visit windows” for analysis purposes. Post-baseline visit windows for each target visit are defined in [Appendix A](#), and will be applied to all measurements. For each summary and value if there are multiple values within a visit window, the “worst” value as defined in [Appendix D](#) will be used for that visit window summary. These visit windows will be applied to all visits, including scheduled, unscheduled, and early termination visits.

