## 7.2 Clinical Laboratory Evaluation

Central laboratory data are transferred electronically by Covance. The Data Transfer Specification document provides a detailed description of the content and format of the laboratory datasets. Both conventional and SI units are provided and will be summarized in separate tables and listings. The eGFR values will be calculated and included in the tables and listings for clinical chemistry parameters.

Results from local laboratories are entered into the CRF by the site; these will not be included in summary tabulations but will be included in the data listings together with the corresponding normal ranges. Values for local laboratory parameters will be converted to the corresponding alternative units, either conventional or SI, depending on how reported.

For the summary tabulations of laboratory results, Baseline is defined as the last non-missing value prior to first dose of study drug in 020. Laboratory tests obtained on the date of the first dose will be assigned to pre-treatment. For each analyte, Baseline values will be restricted to those subjects in the safety population for whom there is at least one post-Baseline value (either overall or for the corresponding target visit). Any lab result 14 or more days after the last dose will be considered post-treatment.

Visit windows are used when results are presented by target visit (see [Appendix A](#)). For each analyte, if a subject has multiple values within a visit window, the “worst” value as defined in [Appendix D](#) will be used for that visit window summary.

Results of all continuous laboratory parameters will be summarized using descriptive statistics at baseline and at each post-baseline target visit; the last available on-treatment value and post-treatment results will also be summarized. The baseline data may come from the prior study, if not repeated in 020. For each subsequent target visit, changes from baseline will also be summarized by the number and percentage of subjects and the mean, median, SD, minimum, and maximum values for continuous laboratory parameters. These will also be prepared for subjects categorized by diagnosis and AChEI/Memantine use.

Box and whisker plots will be presented for selected parameters including hemoglobin, reticulocytes (%), neutrophils, and liver function tests. Other parameters may be identified during data review.

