### 7.3 Vital Signs

Vital sign measurements will be summarized descriptively by target visit using the visit windows defined in [Appendix A](#) and the last available on-treatment visit; baseline will be the last non-missing value prior to the first dose of study drug. The baseline data may come from the prior study, if not repeated in 020. Vital signs include seated blood pressure and pulse, temperature, respiratory rate, and body weight. Change from baseline will also be calculated and summarized. If a subject has multiple values within a visit window, the “worst” value as defined in [Appendix D](#) will be used for that visit window summary.

Potentially clinically significant vital sign changes are defined for selected parameters in [Appendix C](#). When there are thresholds provided for low and high values, they will be handled separately. Summaries will include the number and percent of subjects with treatment-emergent PCS values, restricted to those subjects in whom the values represent a post-baseline worsening (PCST). A PCST is defined as any PCS event that happened at any post-baseline visit and has a value more out of range than the value for a particular parameter at baseline (see [Appendix D](#) for directionality of worsening).

Listings of vital sign measurements including height at Screening will be presented. Listings will flag results that meet criteria as being PCS (whether or not a treatment emergent worsening).

Separate listings for each vital sign parameter will include only subjects with study-emergent PCS values and, for these subjects, all corresponding vital sign results will be provided.

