**APPENDICES**

**Appendix A: Post-Dose Visit Windows**

Visit windows are defined in the following table. Unscheduled and early termination visits are included in the windowing algorithm.

Target Visit	Visit Window Time Interval (Study Day*)	Scheduled Day
Baseline	< 2	NA
Week 2	2 to 53	15
Week 13	54 to 137	92
Week 26	138 to 228	183
Week 39	229 to 319	274
Week 52	320 to 410	365
Week 65	411 to 501	456
Week 78	502 to 591	546
Week 91	592 to 683	637
Week 104	> 683	729
Follow-up	First post-treatment value at least 14 days after last dose	

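### The worst value in each visit window feeds the by-visit means and changes for laboratory, vital sign and ECG data: probably a small shift through Week 91, largest in the open-ended Week 104 row, and in conflict with the protocol only for ECGs done for clinical reasons

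*SAP*

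**What the plan says.** SAP 4.4 assigns all measurements to the Appendix A windows and states: "These visit windows will be applied to all visits, including scheduled, unscheduled, and early termination visits". Appendix A repeats this: "Unscheduled and early termination visits are included in the windowing algorithm". When a window holds more than one value, the rule in 4.4 ("For each summary and value if there are multiple values within a visit window") selects the worst one as defined in Appendix D. SAP 7.2 restates it for laboratory data ("For each analyte, if a subject has multiple values within a visit window") next to the paragraph that specifies by-visit descriptive statistics and changes. SAP 7.3 does the same for vital signs ("If a subject has multiple values within a visit window"). SAP 7.5 puts the ECG descriptive statistics on the same windows, and Appendix D supplies the ECG rule.

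Appendix D has two kinds of rule:
- **One-sided:** lowest hemoglobin, neutrophils and platelets; highest ALT, AST, creatinine, PR, QTcF and QTcB; greatest weight loss.
- **Distance from a reference point:** blood pressure, pulse, WBC, electrolytes, QRS and heart rate.

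Baseline is chosen differently. Under SAP 4.2 it "is the last non-missing value recorded prior to the first dose of study drug in 020". For ECG, the footnote to Table 14.3.4.5.1 makes it the mean of the last triplicate.

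On ECGs, Protocol 9.6.4 says "All other study visit ECG data (interpretations or means of triplicate measurements if" they were done for clinical reasons are to have a separate summary.

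**The concern.** A worst-value rule suits counts of outliers. Used for a mean change, it compares the extreme of several post-baseline readings with one unselected pre-dose reading. For one-sided parameters the difference then moves in the adverse direction with no true change, by an amount that depends on how many values fall in the window. For parameters judged by distance from a reference point, mainly the spread grows, and the sign of any mean shift depends on where the population mean lies.

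By-visit means and changes for hemoglobin, liver tests, QTc, weight and blood pressure are core long-term safety outputs, and long-term safety is a primary objective. Hemolytic anemia is an adverse event of special interest. A drift in the last row of these tables could be read as a late drug effect when it comes from record selection. Nor is the rule uniformly cautious: because worst weight means greatest loss, the weight directional change table would understate gains.

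**Working it through.** **1. Where can a window hold more than one value?** The Appendix A scheduled days are 15, 92, 183, 274, 365, 456, 546, 637 and 729. Midpoints between neighbors are 53.5, 137.5, 228.5, 319.5, 410.5, 501, 591.5 and 683. The stated upper limits are 53, 137, 228, 319, 410, 501, 591 and 683, so the windows reproduce as midpoint windows and each one through Week 91 holds one scheduled visit. A second value there needs an unscheduled, early termination or mistimed visit, and it must be centrally reported: SAP 7.2 keeps local laboratory results out of tabulations and SAP 7.5 only lists local ECGs.

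The Week 104 window is any day after 683, with no upper limit. Protocol 4.3 lets the study run until other access exists, and visits continue every 13 weeks. Days 820 (729 + 91), 911 and 1002 therefore also fall in the Week 104 row. ECGs are scheduled about every 26 weeks, so the extra scheduled ECGs are at days 911, 1093 and 1275.

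**2. Shift for one-sided parameters, no true change.** Mean shift = p × E(k) × s, where p is the share of subjects with k values in the window, s is the within-subject SD, and E(k) is the expected maximum of k independent standard normals: E(2) = 0.564, E(3) = 0.846, E(4) = 1.03. The documents give neither p nor s. Assumed: p from 5% to 30%; s from 8 to 12 msec for QTcF and from 0.4 to 0.6 g/dL for hemoglobin; retesting independent of the result.

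| p (k = 2) | Shift in s | QTcF, msec | Hemoglobin, g/dL |
|---|---|---|---|
| 5% | 0.05 × 0.564 = 0.03 | +0.2 to +0.3 | -0.01 to -0.02 |
| 10% | 0.06 | +0.5 to +0.7 | -0.02 to -0.03 |
| 30% | 0.17 | +1.4 to +2.0 | -0.07 to -0.10 |

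**3. If an abnormal scheduled value triggers the retest.** Simulation with between-subject SD assumed to be 1.5 times s, and a retest for the most adverse 10% or 30% of scheduled values. Relative to using the scheduled value, the shift is 0.018 s and 0.081 s, against 0.056 s and 0.169 s under independence. The scheduled value is itself the worst in 77% and 69% of retested subjects.

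**4. Week 104 row.** For subjects with 2, 3 or 4 scheduled values after day 683, and no unscheduled test at all:

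| k | Shift in s | QTcF, msec | Hemoglobin, g/dL |
|---|---|---|---|
| 2 | 0.56 | +4.5 to +6.8 | -0.23 to -0.34 |
| 3 | 0.85 | +6.8 to +10.2 | -0.34 to -0.51 |
| 4 | 1.03 | +8.2 to +12.4 | -0.41 to -0.62 |

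For hemoglobin, k = 4 is reached at day 1002. For QTcF, k = 2 needs follow-up to day 911 and k = 4 to day 1275.

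**5. Distance-from-reference parameters.** Systolic pressure, reference 125 mmHg, assumed between-subject SD 13 and within-subject SD 9. If every subject has one repeat, the mean shift is about 0, +1.4 or +2.6 mmHg for a population mean of 125, 130 or 135, and the cross-sectional SD rises from 15.8 to between 18.4 and 19.2. With repeats in 10% to 30% of subjects that SD rises by about 2% to 7%. At mean 125 and 30%: √(0.3 × 19.16² + 0.7 × 15.81²) = 16.88, and 16.88 / 15.81 = 1.07.

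**6. ECG text.** The protocol itself generates ECGs for clinical reasons: after a QTcF above 500 msec, Protocol 6.2.3.3 says "repeat ECGs should be obtained, in triplicate, within 2 weeks", and the unscheduled visit in Protocol Appendix A may include a triplicate. Protocol 9.6.4 separates these. SAP 7.5 and Tables 14.3.4.5.1 to 14.3.4.5.3 contain no separate summary, so a centrally read unscheduled ECG enters its window and replaces the scheduled QTc whenever it is higher. SAP Section 9 lists no change from the protocol.

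**7. Gap in the rule.** SAP 4.4 is worded for every summary, but Appendix D defines no worst value for MMSE, eGFR or direct bilirubin, all of which are summarized or plotted by visit.

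**The case against.** The best defense is that the study is single-arm and descriptive. Protocol 9.3.2 plans no inference, so no error rate or decision rule rests on these means. The worst-value rule is pre-specified, and for one-sided parameters it errs towards showing harm. Early termination values were included on purpose, and dropping them would remove discontinuing subjects, possibly in the reassuring direction. All of this stands. It limits the seriousness of the point and shapes the fix, but it does not make an extreme-minus-ordinary difference a fair estimate of mean change.

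Several stronger readings are tempting and should not be drawn.
- **That every by-visit mean is biased.** Appendix D covers only laboratory, vital sign, weight and ECG parameters, and through Week 91 the rule does nothing for a subject with one value per window.
- **That extra values come mostly from unwell subjects.** The protocol arranges unscheduled visits for safety concerns, but the documents give no retest frequency or share by reason. Where a subject is truly unwell, part of the extreme is signal.
- **That the repeat after QTcF above 500 msec greatly inflates QTc.** Such a repeat will often be lower, and the rule then keeps the scheduled reading.
- **That the laboratory and vital sign rules breach the protocol.** Protocol 9.3.2 leaves target windows to the SAP, and the protocol sets no value-selection rule. The conflict is confined to ECG, where it is one missing summary.

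**Conclusion.** The concern holds for laboratory, vital sign, weight and ECG parameters and is worth correcting before the tables are programmed. One-sided parameters shift in the adverse direction wherever a subject has more than one centrally reported value in a window; the others mainly gain spread.

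Through Week 91 the shift is probably small: 0.03 to 0.17 within-subject SD at an assumed 5% to 30% of subjects with a second value, and less if abnormal results prompt the retest. The Week 104 row is the serious case, at 0.56 to 1.03 within-subject SD for subjects with two to four values, because the schedule alone produces the repeats. How far that moves the whole row depends on how many subjects stay beyond about day 820 (day 911 for ECG), which the documents do not say.

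All figures in msec, g/dL and mmHg rest on assumed SDs. The ECG inconsistency with Protocol 9.6.4 rests on the text alone.

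**What to change.** - In SAP 4.4, 7.2, 7.3 and 7.5, for by-visit descriptive statistics and change from Baseline, use one value per window chosen without regard to the result: the scheduled-visit value or, if there are several, the one closest to the Appendix A scheduled day (triplicate mean for ECG). This removes the selection shift and also gives a workable rule for parameters that Appendix D omits.
- When a window has no scheduled value, use the early termination value and, failing that, an unscheduled value, so that discontinuing subjects are kept.
- In Appendix A, close the Week 104 window at its upper midpoint, (729 + 820) / 2 = 774.5, that is day 774, and add later 13-weekly windows.
- Keep the Appendix D worst value for the potentially clinically significant counts and the QTc outlier counts only.
- Add a separate summary of ECGs performed for clinical reasons, as Protocol 9.6.4 states, or declare the change in SAP Section 9.

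The cost is SAP wording, one record-selection rule, extra window rows and one ECG table. By-visit means will no longer reflect the most extreme reading, but that reading stays visible in the outlier tables and listings.

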### **5. STUDY POPULATION**

#### **5.1 Analysis Population**

The safety population is defined as all subjects who received at least one dose of LMTM in 020. Subjects dispensed study medication who subsequently are lost to follow up without any contact are not included in the Safety Population but will be included in the study disposition tabulation and listings. With the exception of study disposition, all tables and listings will be generated on the basis of the Safety Population.

## 5.2 Subject Disposition

Subject disposition information will be summarized for all subjects, overall and by region, country and site. Summaries will include: the number of subjects, (discontinued or completed), all reasons for discontinuation, and the primary reason for discontinuation.

The timing of the early discontinuations will be assessed by summarizing discontinuations by reason during each of the following time periods, overall and by region:

- Day 1
- Days 2 - 53
- Days 54 - 137
- Days 138 - 228
- Days 229 - 319
- Days 320 - 410
- Days 411 - 501
- Days 502 - 591
- Days 592 - 683
- > 683 Days

## 5.3 Protocol Deviations

In accordance with ICH E3, Sponsor-defined eligibility violations and important post-baseline protocol deviations will be identified and listed separately by study site and subject. Sources for these deviations may include IWRS, CTMS (Clinical Trial Management System) and the clinical database. Deviations will be classified as follows:

Deviation type/code as provided by Sponsor:

- Informed consent
- Safety
- IP / Treatment deviation
- Other protocol deviations

Deviations are then categorized into:

- Critical
- Major
- Minor

A tabulation of protocol deviations by type/code overall and by categorization will be provided. A by-subject listing of deviations will also be provided.

#### **5.4 Demographic and Baseline Characteristics**

Tabular summaries of demographics will be prepared based on data collected at the Baseline visit for the prior study and at the baseline for the open-label extension study. These include the following: age, sex, ethnicity, race and geographic region. Age at informed consent for participation in the prior study will be imported into the 020 CRF from IWRS (it is not entered by the site).

General study-specific baseline characteristics to be summarized include the following: height, weight and body mass index (BMI).

Summaries of demographic and baseline characteristics will also be provided by region, country and site.

Additional demographic and baseline characteristics will be presented in a listing only, including childbearing status (for females), main method of adequate contraception, subject's living accommodation, and with whom they live.

